## **END POINTS:**

### ***Primary Outcome Measures:***

1. Change in the International Cooperative Ataxia Rating Scale (ICARS) Score (Baseline – 2 Weeks).
2. Change in the Scale for the Assessment and Rating of Ataxia (SARA) Score (Baseline – 2 Weeks).
3. Change in the Cerebellar cognitive affective syndrome (CCAS) Scale (Baseline – 2 Weeks).

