**INCLUSION / EXCLUSION CRITERIA:** Patients with spino-cerebellar ataxia, Friedreich's ataxia, multisystem atrophy, sporadic ataxia in adult onset will be included. Patients affected by: i) cerebrovascular diseases, hydrocephalus, expansive intracranial processes ii) significant medical problems (eg diabetes and arterial hypertension poorly controlled; cancer in the past 5 years) will be excluded iii) major depressive disorders, bipolar disorders, schizophrenia, abuse of substances, mental retardation according to DSM-IV criteria) implanted metal objects or history of epilepsy. Patients should not suspend any ongoing therapy.

Presidio Ospedaliero  
di Brescia

Regione  
Lombardia  
ASST Spedali Civili

Università  
degli Studi  
di Brescia

CLINICA NEUROLOGICA - UNIVERSITA' DEGLI STUDI DI BRESCIA  
UO Neurologia 2 - AZIENDA SOCIO SANITARIA TERRITORIALE degli SPEDALI CIVILI DI BRESCIA  
Direttore: [name]

**STUDY DESIGN:** this is a randomized, double-blind, non-pharmacologic, placebo-controlled clinical trial, since neither patients nor those who will administer the evaluation tests will be aware of the type of treatment carried out, real-tDCS or sham (anodic tDCS: placebo tDCS = 1: 1) with cerebellar tDCS 5 days a week for 2 consecutive weeks in 40 patients with neurodegenerative ataxia.

A randomized stratification by type of pathology will be implemented, so as to balance the patients with the same pathology between the two groups (real and sham). Subsequently, a randomization in blocks will be implemented, in order to balance the quantitative asymmetry of the patients assigned to the two groups, guaranteeing a similar number of patients enrolled in the two groups, even if the trial should be interrupted early.

Patients with spinocerebellar ataxia, Friedreich's ataxia, multisystem atrophy, sporadic ataxia in adult onset will be included. Each patient will undergo a clinical evaluation (cognitive performance, quality of life and performance of motor coordination and balance), evaluation of CBI connectivity by transcranial magnetic stimulation at baseline (T0), after 2 weeks of treatment with tDCS (T1) and follow -up to 3 months (T2).

An open phase will follow and all patients will receive an anodic tDCS stimulation at the cerebellar and cathodic levels at the spinal level (5 days / week for 2 weeks) and will receive the same standardized evaluation after the 2-week treatment (T3), at the follow- up to 3 months (T4) and 6-month follow-up (T5).

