### ***Secondary Outcome Measures:***

4. Change in the International Cooperative Ataxia Rating Scale (ICARS) Score (Baseline - 2 weeks - 3 month - 6 months - 9 months).
5. Change in the Scale for the Assessment and Rating of Ataxia (SARA) Score (Baseline - 2 weeks - 3 month - 6 months - 9 months).
6. Change in the Cerebellar cognitive affective syndrome (CCAS) Scale (Baseline - 2 weeks - 3 month - 6 months - 9 months).

7. Change in Cerebellar Brain Inhibition (CBI) Measurements (Baseline - 2 weeks - 3 month - 6 months - 9 months).
8. Change in the Short-Form Health Survey 36 (SF36) Score (Baseline - 2 weeks - 3 month - 6 months - 9 months).

**STATISTICAL PLAN:** we will use parametric analyzes (t tests) to compare the demographic variables (age and education) of the two groups at the baseline. A  $P < 0.05$  will be considered significant. To evaluate the effect of the stimulation protocol by means of tDCS on cognitive performances, of motor coordination and balance and quality of life, at T 2-3-4-5 we will use a mixed-model ANOVA.

We performed a "power analysis" to estimate the sample size, based on some previously published studies (Benussi A, Brain Stimul, 2017) using methods similar to those applied in the study in question. The "effect size"  $f(V)$  was calculated by direct method. Taking into account the aforementioned studies an effect size equal to a partial  $\eta^2$  of 0.037, equal to an "effect size"  $f(V)$  of 0.195 and, considering alpha = 0.05 and the power  $(1-\beta) = 0.80$ , the expected sample size is 54 subjects using a repeated measures ANOVA study. The proposed sample size of 60 subjects should be adequate to achieve the main objective of the study.

**ETHICAL CONSIDERATIONS (RISK-BENEFIT):** tDCS is a non-invasive, low-cost and easy-to-implement method which is having an increasing diffusion and an increasingly numerous spectrum of potential therapeutic applications such as, for example, post-stroke rehabilitation, depression and pain, already consolidated. Recently its efficacy in modulating cerebellar excitability in humans (Galea 2009) has been demonstrated with favorable effect of cerebellar anodic stimulation by tDCS on motor learning and walking (Jayaram 2012).

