We therefore hypothesize that tDCS may have a positive effect on the performance of motor coordination and balance in patients with Spinocerebellar Atrophy, a group of neurodegenerative pathologies characterized by slowly progressive ataxia of walking, posture and limbs, associated with dysarthria and / or alteration of oculomotor, for which currently no treatments are available.

Literature data show that the application of the method according to the current safety guidelines (Iyer, 2005; Nitsche, 2003; Wassermann 2005) has little relevant side effects, including mild tingling sensation during or after stimulation, moderate fatigue, slight sensation of itching at the electrode application points, slight burning or pain, headache, nervousness, nausea, appearance of vesicles at the electrode application points in more rare cases.

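### Three unranked primary outcomes have no success rule or multiplicity adjustment; if each is tested at 0.05 and any one counts, the false-positive risk is about 8–13% under assumed correlations

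*Combined protocol and SAP*

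**What the plan says.** Under END POINTS, the Primary Outcome Measures are "Change in the International Cooperative Ataxia Rating Scale (ICARS) Score (Baseline – 2 Weeks"), "Change in the Scale for the Assessment and Rating of Ataxia (SARA) Score (Baseline – 2 Weeks") and "Change in the Cerebellar cognitive affective syndrome (CCAS) Scale (Baseline – 2 Weeks"). All three refer to the visit that STUDY DESIGN places "after 2 weeks of treatment with tDCS (T1"). They are numbered 1 to 3, but the numbering runs on through the secondary outcomes to 8, so it is not a testing order.

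STATISTICAL PLAN gives a level of 0.05 in two places. A P value below 0.05 "will be considered significant" in the sentence that follows the baseline t tests. The sample-size calculation is made "considering alpha = 0.05 and the power" at 0.80. That single calculation returns 54 subjects, and the proposed 60 "should be adequate to achieve the main objective of the study". It is not tied to any of the three scales.

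The outcomes are to be analysed by mixed-model ANOVA. The protocol contains no success rule, hierarchy, composite or adjustment across outcomes.

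**The concern.** A trial with three primary outcomes needs a rule that turns three P values into one conclusion. Without it, the error rate and the power of the primary claim are undefined.

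- **Any one suffices, each at 0.05.** The chance of a false positive on at least one scale exceeds the 5% used for sizing.
- **All three required.** There is no inflation, but power is lower than for a single outcome at the same sample size, so the planned 80% does not describe it.
- **No rule.** The reading can be chosen once the results are known.

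The third case has a concrete form here. The ETHICAL CONSIDERATIONS section states a motor hypothesis ("We therefore hypothesize that tDCS may have a positive effect on the performance of motor coordination and balance"), while OBJECTIVES also names cognition and quality of life, and CCAS is a cognitive-affective scale. If CCAS were positive and both ataxia scales null, the plan does not say whether the trial succeeded.

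**Working it through.** **Inputs from the protocol.** Three primary outcomes; alpha 0.05; power 0.80; f(V) = 0.195; calculated N = 54; 1:1 allocation. The planned size is 40 in STUDY DESIGN and 60 in STATISTICAL PLAN. That conflict is a separate matter, so both sizes are used.

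**Assumptions not in the protocol.** Two-sided tests; a between-group comparison of change at 2 weeks; all correlations between the scales; the number of time points m; and the correlation rho between a patient's repeated measurements.

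**1. Reproducing the 54.** For a group-by-time interaction with two groups, take

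lambda = f² × N × m / (1 − rho).

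With m = 2 and rho = 0.5, N = 54 gives lambda = 0.195² × 54 × 2 / 0.5 = 8.21 and power 0.803, which matches. With rho = 0.4 the required N is 64, and with rho = 0.6 it is 44. The alternative convention lambda = f² × (N − 2) × (m − 1) needs 212 patients and does not reproduce 54. On it, power at N = 60 would be 0.31 at level 0.05 and 0.17 at 0.0167.

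**2. False-positive risk if any one counts.** Under independence it is 1 − 0.95³ = 0.143. For correlated scales, null trials with N = 40 were simulated (400,000 per setting, two-sample t tests on change). N = 60 agrees within 0.001.

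| ICARS–SARA correlation | CCAS with each | P(at least one p < 0.05) |
|---|---|---|
| 0.7 | 0.3 | 0.126 |
| 0.8 | 0.3 | 0.121 |
| 0.9 | 0.3 | 0.114 |
| 0.7 | 0.5 | 0.120 |
| 0.9 | 0.5 | 0.109 |
| 0.8 | 0.8 | 0.099 |
| 0.9 | 0.9 | 0.084 |

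With CCAS correlation 0.3, CCAS alone is significant in 4.2–4.3% of null trials. Holm at an overall 0.05 brings the chance of any false positive to 3.0–4.9%.

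**3. Power for one outcome** (m = 2; rho = 0.4 / 0.5 / 0.6).

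| N | At 0.05 | At 0.05/3 = 0.0167 |
|---|---|---|
| 40 | 0.593 / 0.671 / 0.767 | 0.410 / 0.492 / 0.602 |
| 60 | 0.774 / 0.844 / 0.913 | 0.616 / 0.710 / 0.816 |

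**4. Power if all three are required**, each at 0.05, with equal effects on all scales, ICARS–SARA correlation 0.7–0.9, CCAS correlation 0.3 and rho 0.4–0.6: 0.325–0.578 at N = 40 and 0.560–0.819 at N = 60.

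**5. Power if any one suffices**, with equal effects, N = 60, rho = 0.5 and the same between-scale correlations: about 96–97% unadjusted and 90–92% with Holm. With all correlations at 0.9, Holm gives about 80%.

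**The case against.** **Inflation is not established.** It requires the any-one reading and the use of 0.05 for each primary outcome. That level is written beside the baseline tests and in the sizing, so its use here is inferred. This stands. It makes the inflation a risk and leaves the gap in place, because nothing in the protocol excludes the any-one reading.

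**The 8–13% depends on chosen correlations.** This also stands: the protocol gives none. Weaker correlations give more (13.6% if all are 0.3, 14.3% under independence). Only near-perfect correlation of all three brings the rate back to 5%, and overlap between ICARS and SARA alone does not, because CCAS still adds a separate chance.

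**The rate counts results in both directions.** The stated hypothesis is of benefit. Counting only false positives in favour of tDCS, the risk is about 4.2–6.5% for common correlations from 0.9 down to 0.4, against a nominal 2.5%. This is a fair qualification, but the relative inflation is similar: 4.2/2.5 = 1.7 to 6.5/2.5 = 2.6 times.

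**Adjustment looks costlier than it is.** The fall from 84% to 71% is for one given scale at the first Holm step. If all scales respond equally, the chance of at least one success falls only from 96–97% to 90–92%. This is correct and favours Holm as an inexpensive choice.

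**The analysis itself is uncertain.** STATISTICAL PLAN applies the mixed-model ANOVA to T2 to T5 and does not name T1, where the primary outcomes are measured. The calculations assume a T1 comparison. That gap needs its own correction.

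**Conclusion.** The concern holds. The three primary outcomes have no ranking, success rule or multiplicity adjustment, and no other section supplies one. If each is tested at two-sided 0.05 and any one counts, the false-positive risk is about 8–13% for the assumed correlations, with 14.3% as the independence limit. If all three are required there is no inflation. Power is then 56–82% at N = 60 and 33–58% at N = 40, against 77–91% and 59–77% for one outcome alone. It need not fall below 80%: at N = 60 and rho = 0.5, with all between-scale correlations at 0.97, it is 0.807.

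The missing rule is plain from the text. The error rates rest on assumed correlations. The power figures rest also on equal effects and on the reading of f(V) that returns 54. The point should be corrected before unblinding; as inflation depends on a reading the plan leaves open, it does not by itself invalidate the trial.

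**What to change.** Before unblinding, add one success rule for the between-group comparison of change from baseline at T1. Any of these is valid:

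- **(a) Any one suffices.** *Change in ICARS, SARA and CCAS will be tested with the Holm procedure at an overall two-sided alpha of 0.05.*
- **(b) One lead outcome.** *The primary outcome is change in [named scale], tested at two-sided 0.05; the other two scales are supportive.* The sponsor must choose the scale, since the stated hypothesis is motor while OBJECTIVES also includes cognition.
- **(c) All required.** *The trial is positive only if all three outcomes are significant at two-sided 0.05.*

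Report secondary outcomes as supportive. Restate the power for the chosen rule, giving its assumptions and the sample size that applies.

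The change needs one sentence and one recalculated figure, and no new data; no extra patients are requested. Each rule has a price:

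- **(a)** lowers power for a given scale at the first step (84% to 71% at N = 60, m = 2, rho = 0.5; 62–82% for rho 0.4–0.6). Keeping 80% for one given scale at 0.0167 would take 72 patients on the same assumptions. It also allows a positive trial on CCAS alone.
- **(b)** gives up a confirmatory claim on the other two scales.
- **(c)** has the lower all-three power given above.

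Once the data are unblinded, a rule can no longer be shown to be independent of the results.

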### ***Secondary Outcome Measures:***

4. Change in the International Cooperative Ataxia Rating Scale (ICARS) Score (Baseline - 2 weeks - 3 month - 6 months - 9 months).
5. Change in the Scale for the Assessment and Rating of Ataxia (SARA) Score (Baseline - 2 weeks - 3 month - 6 months - 9 months).
6. Change in the Cerebellar cognitive affective syndrome (CCAS) Scale (Baseline - 2 weeks - 3 month - 6 months - 9 months).

7. Change in Cerebellar Brain Inhibition (CBI) Measurements (Baseline - 2 weeks - 3 month - 6 months - 9 months).
8. Change in the Short-Form Health Survey 36 (SF36) Score (Baseline - 2 weeks - 3 month - 6 months - 9 months).

**STATISTICAL PLAN:** we will use parametric analyzes (t tests) to compare the demographic variables (age and education) of the two groups at the baseline. A  $P < 0.05$  will be considered significant. To evaluate the effect of the stimulation protocol by means of tDCS on cognitive performances, of motor coordination and balance and quality of life, at T 2-3-4-5 we will use a mixed-model ANOVA.

We performed a "power analysis" to estimate the sample size, based on some previously published studies (Benussi A, Brain Stimul, 2017) using methods similar to those applied in the study in question. The "effect size"  $f(V)$  was calculated by direct method. Taking into account the aforementioned studies an effect size equal to a partial  $\eta^2$  of 0.037, equal to an "effect size"  $f(V)$  of 0.195 and, considering alpha = 0.05 and the power  $(1-\beta) = 0.80$ , the expected sample size is 54 subjects using a repeated measures ANOVA study. The proposed sample size of 60 subjects should be adequate to achieve the main objective of the study.

**ETHICAL CONSIDERATIONS (RISK-BENEFIT):** tDCS is a non-invasive, low-cost and easy-to-implement method which is having an increasing diffusion and an increasingly numerous spectrum of potential therapeutic applications such as, for example, post-stroke rehabilitation, depression and pain, already consolidated. Recently its efficacy in modulating cerebellar excitability in humans (Galea 2009) has been demonstrated with favorable effect of cerebellar anodic stimulation by tDCS on motor learning and walking (Jayaram 2012).

We therefore hypothesize that tDCS may have a positive effect on the performance of motor coordination and balance in patients with Spinocerebellar Atrophy, a group of neurodegenerative pathologies characterized by slowly progressive ataxia of walking, posture and limbs, associated with dysarthria and / or alteration of oculomotor, for which currently no treatments are available.

Literature data show that the application of the method according to the current safety guidelines (Iyer, 2005; Nitsche, 2003; Wassermann 2005) has little relevant side effects, including mild tingling sensation during or after stimulation, moderate fatigue, slight sensation of itching at the electrode application points, slight burning or pain, headache, nervousness, nausea, appearance of vesicles at the electrode application points in more rare cases.

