## EXPERIMENTAL CLINICAL PROTOCOL

**TITLE OF THE STUDY:** “Cerebello-Spinal tDCS as Rehabilitative Intervention in Neurodegenerative Ataxia”

**ACRONYM:** SCA02

**VERSION AND DATE:** Version 2 of September 4, 2018

**DIVISION WHERE THE RESEARCH IS PERFORMED:** Clinica Neurologica, Università di Brescia, Spedali Civili di Brescia

**MAIN EXPERIMENTATOR:** [name]

**INTRODUCTION AND RATIONAL:** Transcranial stimulation with direct currents or transcranial direct current stimulation, tDCS is a neurophysiological method of non-invasive modulation of the central nervous system excitability, which is having an increasing diffusion and an increasingly numerous spectrum of potentials therapeutic applications such as, for example, post-stroke rehabilitation, depression and pain, already consolidated. This method, being non-invasive, low-cost and simple to carry out, has the potential to be widely used both as a research tool and as a support tool for rehabilitation treatment, as in the case of Spinocerebellar Ataxias, a group of neurodegenerative pathologies based on genetics, characterized by slowly progressive ataxia of walking, posture and limbs, associated with dysarthria and / or alteration of oculomotion, for which no treatments are currently available. This method also finds application in Cerebellar Ataxias of neurodegenerative origin, such as in Multisystem Atrophy (MSA), in Friedreich Ataxia and in other Central Nervous System pathologies with selective involvement of cerebellar structures. Indeed, a positive effect of tDCS has been demonstrated in modulating cerebellar excitability in humans (Galea 2009) with a favorable effect of cerebellar anodic stimulation by tDCS on motor learning and walking (Jayaram 2012). Based on these premises, the treatment of patients with Cerebellar Ataxias of neurodegenerative origin is proposed (for example SCA, MSA, Friedreich's Ataxia).

Transcranial magnetic stimulation (TMS) techniques have been widely used in the study of neurodegenerative diseases, particularly in Parkinson's disease and dementia due to Alzheimer's disease. Over the years, numerous transcranial magnetic stimulation protocols have been developed to obtain information on neurophysiological parameters

with the aim of investigating both the pathogenesis and the evolution of some neurodegenerative pathologies.

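### The 6- and 9-month parts of secondary endpoints 4-8 are not sham-controlled, yet the plan judges the tDCS effect in one ANOVA over T2-T5, three of whose four visits follow real tDCS in both arms

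*Combined protocol and SAP*

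**What the plan says.** STUDY DESIGN sets the blinded assessments "at baseline (T0), after 2 weeks of treatment with tDCS (T1) and follow -up to 3 months (T2"). It then states: "An open phase will follow and all patients will receive an anodic tDCS stimulation", with further assessments "after the 2-week treatment (T3), at the follow- up to 3 months (T4) and 6-month follow-up (T5"). The former sham arm thus receives its first real course and the real arm its second.

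Under END POINTS, items 4-8 (ICARS, SARA, CCAS, CBI and SF36) share one time pattern, as in "Change in the Short-Form Health Survey 36 (SF36) Score (Baseline - 2 weeks - 3 month - 6 months - 9 months"). Only one baseline is named.

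The STATISTICAL PLAN says that, to evaluate the effect of the stimulation protocol, "at T 2-3-4-5 we will use a mixed-model ANOVA". It defines no contrast for the visits after the open course and no reference visit for the open phase.

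OBJECTIVES gives long-term effects as the aim. The introduction describes the spinocerebellar ataxias as "characterized by slowly progressive ataxia of walking, posture and limbs".

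**The concern.** The endpoint list and the ANOVA run the sham-controlled and open phases together, as if one treatment comparison applied throughout. It does not: after T2 no arm is without real tDCS.

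Two misreadings follow. First, a small between-arm difference at 6 or 9 months could be taken as fading benefit when it reflects the former sham arm's own treatment. Second, change from T0 in the former sham arm could be taken as the effect of the open course. It also contains sham response, repeat testing and about three months of disease course. In the real-first arm, change from T0 mixes two courses.

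The visit lists also disagree. T3 closes the open course and is in the ANOVA but in no endpoint. T0 and T1 are in the endpoints but not in the ANOVA. At stake is what the trial may conclude about long-term effect, which is its stated aim.

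**Working it through.** The plan gives no figure on durability or on the open phase. Its one computed figure, the sample size of 54, does not enter this point.

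**Visits side by side** (STUDY DESIGN; END POINTS items 4-8; STATISTICAL PLAN). Times assume that the open course starts at T2.

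| Visit | Approx. time | Real courses so far (real arm / sham arm) | In items 4-8 | In ANOVA |
|---|---|---|---|---|
| T0 | 0 | 0 / 0 | yes | no |
| T1 | 2 weeks | 1 / 0 | yes | no |
| T2 | 3 months | 1 / 0 | yes | yes |
| T3 | 3.5 months | 2 / 1 | no | yes |
| T4 | 6 months (6.5 if counted from the end of the open course) | 2 / 1 | yes | yes |
| T5 | 9 months (9.5) | 2 / 1 | yes | yes |

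Two of the four post-baseline times in items 4-8, and three of the four ANOVA visits, come after both arms have had real tDCS. The lists share only T2, T4 and T5. Neither contains both T0-T1 and T2-T3, the two matching before-and-after windows in the sham-first patients.

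**What the later contrasts measure.** Assume that a course gives benefit D at its end, that a fraction r remains 3 months later (r² at 6, r³ at 9), that sham gives none, and that disease course and retest effects are equal in both arms. The two-week course length is ignored. The documents give no value for r.

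*If course effects add:*
- T2: rD − 0 = rD (sham-controlled)
- T3: (D + rD) − D = rD
- T4: (rD + r²D) − rD = r²D
- T5: (r²D + r³D) − r²D = r³D

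These equal what is left of course 1 at each visit. Under additivity the contrast does measure durability.

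*If there is a ceiling, so that a patient has only the larger current course effect:*
- T3: D − D = 0
- T4: rD − rD = 0
- T5: r²D − r²D = 0

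| r | T4 contrast, additive | T5 contrast, additive | T4 and T5 contrast, ceiling |
|---|---|---|---|
| 1 | D | D | 0 |
| 0.75 | 0.56D | 0.42D | 0 |
| 0.5 | 0.25D | 0.125D | 0 |
| 0.25 | 0.06D | 0.02D | 0 |

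At r = 1 nothing has faded, yet the contrast is D or 0 depending on an assumption that the plan does not state. If a second course does more than a first, the error goes the other way: the contrast exceeds what is left of course 1. No arm receives course 1 without the open course, so these cases cannot be told apart at T4 and T5.

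**What change from T2 measures** (additive case):
- Sham-first arm: D at T3, rD at T4, r²D at T5, plus any disease course and retest effect.
- Real-first arm, T4: (rD + r²D) − rD = r²D, whereas course 2 alone contributes rD. At r = 0.5 this is 0.25D against 0.5D.
- Real-first arm, T5: (r²D + r³D) − rD. At r = 0.5 this is 0.25D + 0.125D − 0.5D = −0.125D, whereas course 2 alone contributes 0.25D.

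T2 as reference therefore gives a cleaner reading only in the sham-first arm. In the real-first arm, carry-over from course 1 remains in the change.

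**The case against.** The best defence is that the randomized arms still differ at T4 and T5 and that, if course effects add, their difference is exactly what remains of the randomized course. This is right as far as it goes, and it limits the point: the late contrast depends on an assumption but is not empty.

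A reader might go further and infer that items 4-8 show no long-term effect at all. The documents do not support that. T2 precedes the open phase and gives a randomized, blinded test of persistence to 3 months. A reader might also express the late contrast as a share of the total benefit of two courses over no tDCS and call the rest hidden. The documents never set that total as a target. Nor is T3 ignored: it is assessed and named in the ANOVA, so the defect is a mismatch between lists. Change from T2 can be computed from data already planned.

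Two further objections have some force. The time pattern in items 4-8 could be a list of visits rather than a set of changes from T0, and the match of 6 and 9 months to T4 and T5 is inferred, although the schedule has no other visits near those times. The protocol also calls the period an open phase and nowhere claims sham-controlled efficacy at 6 or 9 months. Against this, the STATISTICAL PLAN uses a single model over T2-T5 to evaluate the stimulation effect and does not separate the phases.

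**Conclusion.** The point holds for the 6- and 9-month parts of items 4-8 and for the ANOVA visit list. After T2 the between-arm contrast is two courses versus one delayed course, and it can be read as durability of the first course only under additivity. For a fully lasting benefit it could be anything from D (additive) to zero (ceiling), so a null late contrast would not show fading. That range rests on the simple decay model above and is illustrative.

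The T2 component stands as a sham-controlled result. The primary endpoints, defined from baseline to 2 weeks, lie wholly within the blinded phase and are unaffected. The problem is confined to secondary endpoints, but it should be settled before analysis because it decides what may be said about the trial's long-term aim.

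**What to change.** Amend END POINTS and the STATISTICAL PLAN as follows:

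1. For items 4-8, limit real-versus-sham inference to T1 and T2, with T0 as baseline.
2. Report the open phase separately by original arm, as change from T2 to T3, T4 and T5, and add T3 to the endpoint list.
3. In the sham-first arm, show T2-T3 beside the same patients' T0-T1, labelled as an open-label, within-patient comparison without a concurrent control.
4. State that in the real-first arm change from T2 still contains carry-over from course 1.
5. Label between-arm differences at T3-T5 as two courses versus one delayed course, interpretable as durability only if course effects add.
6. Reconcile the endpoint and ANOVA visit lists, so that T0, T1 and T3 each have a stated role, and state which visits are the 6- and 9-month time points.

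The cost is amendment wording and a few tabulations, with no new visit, test or patient. The sponsor gives up a sham-controlled claim at 6 and 9 months, which the design cannot support in any case.

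### By the protocol's own visit labels, the only efficacy analysis omits the 2-week visit of all three primary endpoints; if the labels are a slip, the primary test is still unnamed and open-phase visits share the model

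*Combined protocol and SAP*

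**What the plan says.** Three parts of the combined protocol and SAP bear on this point.

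- **Study Design** holds the only visit labels. T0 is baseline, and the next visits are "after 2 weeks of treatment with tDCS (T1) and follow -up to 3 months (T2"). In this phase "neither patients nor those who will administer the evaluation tests will be aware of the type of treatment carried out, real-tDCS or sham". Then "An open phase will follow and all patients will receive an anodic tDCS stimulation", with assessments "after the 2-week treatment (T3), at the follow- up to 3 months (T4) and 6-month follow-up (T5").
- **End Points, Primary Outcome Measures** lists three items, all over the same window: "Change in the International Cooperative Ataxia Rating Scale (ICARS) Score (Baseline – 2 Weeks"), "Change in the Scale for the Assessment and Rating of Ataxia (SARA) Score (Baseline – 2 Weeks") and "Change in the Cerebellar cognitive affective syndrome (CCAS) Scale (Baseline – 2 Weeks"). The secondary list gives five time points: baseline, 2 weeks, and 3, 6 and 9 months.
- **Statistical Plan** describes one efficacy analysis, covering cognition, coordination and balance, and quality of life: "at T 2-3-4-5 we will use a mixed-model ANOVA". The only other tests named are t tests of age and education at baseline. The model terms are not given. No sentence names the primary test or separates the two phases.

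**The concern.** Read with the protocol's own labels, the analysis set is T2, T3, T4 and T5. It leaves out T1, the visit that defines every primary endpoint. T0 is not listed either, though it may enter as the reference for change. Of the four visits, only T2 is sham-controlled. By T3 the original sham arm has had active stimulation, so a comparison of the randomised arms at T3 to T5 is two active courses against sham followed by one active course.

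If the labels are a slip and the 2-week visit is included, two gaps remain. A mixed-model ANOVA offers a group term, a group-by-visit term and single-visit contrasts, and the plan does not say which one answers the primary question. Also, the sham-controlled phase has only T0, T1 and T2, so any four-visit model must include at least one open-phase visit. The result for a 2-week endpoint could then depend on events after the sham arm is treated, and the term could be chosen after the data are seen.

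**Working it through.** **1. Labels side by side**

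| Label (Study Design) | Timing | Phase | In T2–T5? |
|---|---|---|---|
| T0 | baseline | sham-controlled | no |
| T1 | after 2 weeks of treatment | sham-controlled | **no** (primary visit) |
| T2 | 3 months | sham-controlled | yes |
| T3 | after open 2-week course | open | yes |
| T4 | 3 months, open phase | open | yes |
| T5 | 6 months, open phase | open | yes |

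**2. The slip reading.** Counting the five secondary time points from 1 makes points 2 to 5 equal to 2 weeks, 3, 6 and 9 months, which covers the 2-week visit. But Study Design has six visits, so the lists do not match one to one. Reading 6 and 9 months as T4 and T5 leaves T3 without a place.

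**3. The plan's own sample size.** Inputs from the Statistical Plan: f = 0.195, alpha 0.05, power 0.80, N = 54. For a group-by-time test with 2 groups and m measurements with correlation ρ:

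λ = N·m·f²/(1−ρ), df = (m−1) and (N−2)(m−1).

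With m = 2 and ρ = 0.5 (neither is stated), λ = N × 2 × 0.038025/0.5 = 0.1521·N. At N = 54, λ = 8.21 and power is 0.803; 54 is the smallest even N reaching 0.80. So 54 fits a T0–T1 contrast. With ρ = 0.5, m = 4 gives 38. Other pairs also give 54 (m = 3 with ρ = 0.4, for example), so this suggests a slip but does not prove one.

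**4. Implied 2-week effect.** Setting 0.1521·N = N·d²/4 gives d² = 0.6084 and d = 0.78, in SDs of T0–T1 change. With ρ from 0.4 to 0.6, d runs from 0.71 to 0.87.

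**5. Power by choice of term, slip reading.** Assumptions: changes from baseline with SD 1, compound symmetry (so changes correlate 0.5), and the full difference at 2 weeks and 3 months. At 6 and 9 months none, half or all of it is left. The pattern e is (1,1,0,0), (1,1,½,½) or (1,1,1,1), with mean ē.

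- T0–T1 contrast: λ = N·d²/4, df 1, N−2.
- Group term: λ = (N/4)(d·ē)²/0.625, where 0.625 = (1 + 3×0.5)/4; df 1, N−2.
- Group-by-visit, four changes: λ = (N/4)d²·Σ(e−ē)²/0.5, df 3, 3(N−2).
- Group-by-visit with T0 as a fifth level: same form with a 0 added to e, df 4, 4(N−2).

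Example, N = 40, pattern (1,1,0,0), group term: ē = 0.5 and λ = 10 × 0.39²/0.625 = 2.43, so power is 0.330. For the four-change interaction, Σ(e−ē)² = 1 and λ = 10 × 0.6084/0.5 = 12.17, so power is 0.832.

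| Test | N=40: none / half / all | N=60: none / half / all |
|---|---|---|
| T0–T1 contrast | 67% in each | 84% in each |
| Group term | 33 / 63 / 86% | 47 / 80 / 96% |
| Group-by-visit, four changes | 83 / 27 / 5% | 96 / 40 / 5% |
| Group-by-visit with T0 | 87 / 62 / 69% | 97.5 / 82 / 87% |

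Both sizes are shown because Study Design gives 40 and the Statistical Plan gives 60. A simulation of 8,000 runs agreed with the first three rows.

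**6. Literal reading (T2–T5).** A difference present only at T1 reaches P<0.05 in 5% of trials at any N, because T1 is not in the data analysed. If the full difference is present at T2 and none, half or all of it at T3–T5, the group term gives 12 / 48 / 86% at N = 40 and 16 / 65 / 96% at N = 60. Those tests address later visits, not the primary endpoint.

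**The case against.** The strongest reply is that this is a labelling slip. The five time points stand just above the sentence at issue, numbering them from 1 restores the 2-week visit, and the stated 54 fits a two-measurement design. The scales, window, arms and 1:1 allocation are already fixed, so a reader could infer the primary contrast. This makes the slip plausible, perhaps likely. It does not supply the missing statement of the primary test, and the written labels still contradict it.

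On the figures, four criticisms are fair:

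- The 5% in the literal reading is true by construction, and the Objectives section speaks of long-term effects, so an effect confined to T1 is not the plan's hypothesis.
- The most conventional model, group-by-visit with T0 as a level, has power near or above the T0–T1 contrast in every case shown. With that model the problem is mainly interpretation: a significant result need not mean a 2-week effect.
- The value d = 0.78 rests on an unstated correlation. If the partial eta squared of 0.037 described the two-visit interaction directly, d would be about 2 × 0.195 = 0.39, and T0–T1 power about 22% at N = 40 and 31% at N = 60. That reading does not reproduce 54 (it needs 212).
- Pooling of the phases is inferred from one ANOVA being named for all these visits; the plan does not say that T3–T5 will be read as active versus sham.

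None of these removes the contradiction or names the primary test.

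**Conclusion.** The concern holds on both readings. Taken literally, the plan tests none of its three primary endpoints, and three of its four analysed visits lack a concurrent sham group. This follows from the text alone. Read as a slip, the 2-week visit is covered, but the primary test is not identified and the one model described spans both phases.

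The size under the slip reading is illustrative. For one fixed 2-week effect at N = 40, the chance of P<0.05 runs from 5% to 87% according to the term chosen and what happens in the open phase, while the T0–T1 contrast stays at 67%. At N = 60 the range is 5% to 97.5% against 84%. These percentages depend on d = 0.78, compound symmetry, analysis of change and the mapping of 6 and 9 months to T4 and T5. With d from 0.71 to 0.87, the T0–T1 power at N = 40 is 59% to 77%. The point is the dependence on an unstated choice, not the exact values. It must be fixed, because a confirmatory randomised trial has to identify its primary test in advance.

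**What to change.** **Must fix**

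1. Correct the visit labels in the Statistical Plan so that they agree with Study Design and with the secondary time points, and give T3 a place. In doing so, reconcile the timing of the 2-week visit: Procedures puts it two weeks after treatment, Study Design at the end of two weeks of treatment.
2. State that the primary analysis of ICARS, SARA and CCAS is active versus sham on T0–T1 change, or on T1 adjusted for T0.

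**Should fix**

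3. Limit active-versus-sham inference to T0–T2.
4. Report T3–T5 separately by original sequence, labelled as two active courses versus sham then one active course.

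The cost is wording in the Statistical Plan. No visit or measurement is added, since T0, T1 and T2 are already scheduled. Under the assumptions that reproduce 54, naming the T0–T1 contrast leaves that requirement unchanged, before any allowance for having three primary endpoints.
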